6.4. Global Statistical Test

The following endpoints will be included in the GST and will be considered as an exploratory analysis. The number of skills gained and number of skills improved or maintained will not be included in the GST as they are derived from the same 17 individual NSAA skills that contributed to the NSAA total score.

- Change from Baseline at Week 52 in the NSAA total score.
- Change from Baseline at Week 52 in the 10 meter run/walk test velocity.
- Change from Baseline at Week 52 in the rise from floor velocity.
- Change from Baseline at Week 52 in the 95th percentile of cadence.

Analysis set: FAS ([Section 4](#)).

- Analysis methodology: The GST will be conducted as described in [Section 5.2.4](#) by combining summary statistics for select functional endpoints listed above into a single global test statistic.
- For each endpoint, the estimated group difference from MMRM, the corresponding standard error, and standardized z score will be provided. The mean observed z score across multiple endpoints, and p-value for the GST will be provided.

6.5. Subset Analyses

Subgroup analyses based on Screening age strata, Baseline NSAA Total score, and Geographic region strata will be performed for primary efficacy endpoint and the select secondary efficacy endpoints.

6.5.1. Screening Age Strata

The following endpoints will be evaluated by two screening age strata (<6 years and ≥ 6 years):

- Change from Baseline at Week 52 in the NSAA total score.
- Change from Baseline at Week 52 in the 10 meter run/walk test velocity.
- Change from Baseline at Week 52 in the rise from floor velocity.
- Number of skills gained at Week 52 based on the individual items of the NSAA.
- Number of skills either improved or maintained at Week 52 based on the individual items of the NSAA.
- Change from Baseline at Week 52 in the 95th percentile of cadence.

The age strata at screening (Randomization Group) collected in the clinical database will be used for subset analysis.

- Analysis set: FAS ([Section 4](#)).
- Analysis methodology:
 - The analysis methods for the main analysis of primary endpoint in [Section 6.1](#) and the secondary endpoints in [Section 6.2](#) will be applied for the subset analysis, where the model will be handled in a different way as below:
 1. Analysis for the endpoints change from Baseline at Week 52 in the NSAA total score, 10 meter run/walk test velocity, rise from floor velocity, and 95th percentile of cadence.

- For each Screening age strata separately, change from baseline will be analyzed using an MMRM approach ([Section 5.2.1.1](#)) including visits through Week 52 with additional fixed effects for Baseline(continuous variable), and Baseline by visit interaction.

For each Screening age strata, estimates of the mean changes from Baseline, standard error of each LS mean, and 95% confidence intervals for fordadistrogene movaparvovec and placebo will be provided for each visit along with the mean treatment group difference and the corresponding standard error, two-sided p-value, and two-sided 95% confidence interval for the mean difference at each visit.

- Change from baseline will be analyzed using an MMRM approach ([Section 5.2.1.1](#)) including visits through Week 52 with additional fixed effects for Baseline (continuous variable), Baseline by visit interaction, Screening age strata (binary variable), Screening age strata by visit interaction, and Screening age strata by treatment group interaction.

The p-value for the Screening age strata interaction term will be provided.

2. Analysis for endpoints number of skills gained and number of skills either improved or maintained at Week 52

- For each subset separately, the number of skills will be analyzed using the approach described in [Section 5.2.3](#).
- For each subset, estimates of the LS means and 95% confidence intervals for fordadistrogene movaparvovec and placebo will be provided along with the difference in LS means and corresponding standard error, two-sided p-value, and two-sided 95% confidence interval for the mean difference.
- The number of skills will be analyzed using the approach described in [Section 5.2.3](#) with fixed effects for Screening age strata (categorical variable) instead of age model covariate, and Screening age strata by treatment group interaction. The p-value for the Screening age strata by treatment group interaction term will be provided.

- Intercurrent events and missing data: All available data in the reporting period will be included. The intercurrent events and missing data will be handled as described in [Section 2.2.1](#) and [Section 2.2.2](#) accordingly.

- For each Screening age strata separately, the summary for each endpoint will be performed the same way as described in the corresponding main analysis in [Section 6.1](#) and [Section 6.2](#).

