3.4. Baseline Variables

3.4.1. Covariates and Stratification Variables

- Baseline for the primary endpoint: Baseline NSAA total score is defined as the last non-missing NSAA total score collected prior to Year 1 IP administration.
- Baseline for secondary and exploratory endpoints: Baseline is defined as the last non-missing assessment collected prior to Year 1 IP administration.
- Screening age (years) covariate: The screening age covariate is defined as the participant's age (as calculated based on month and year of birth) on the day of the Screening visit. Screening age will be calculated to one decimal (eg, 7 years and 4 months will be 7.3 years).
- The participant's Screening age rather than Screening age stratum will be used in all efficacy analyses, unless specified otherwise.

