6.1.1.1. Main Analysis

- Estimand strategy: Primary Estimand ([Section 2.2.1](#)).
- Analysis set: FAS ([Section 4](#)).
- Analysis methodology: Change from baseline will be analyzed using an MMRM approach ([Section 5.2.1.1](#)) including visits through Week 52 where NSAA is assessed (ie, Weeks 9, 18, 35, 52) with additional fixed effects for Baseline NSAA total score (continuous variable), Screening age (continuous variable), Baseline NSAA total score by visit interaction, and Screening age covariate by visit interaction.

To test the primary hypothesis, estimates from the MMRM analysis at Week 52 of the mean changes from Baseline, standard error of each LS mean, and 95% confidence intervals along with the mean treatment group difference, two-sided p-value, and two-sided 95% confidence interval for the mean difference will be provided.

- Intercurrent events and missing data: All available data in the reporting period will be included. The intercurrent events (loss of ambulation or death) and missing data from study discontinuation will be handled in the Primary Estimand as described in [Section 2.2.1](#).
- The number of participants (N), mean, standard deviation (SD), median, first quartile (Q1), third quartile (Q3), minimum, and maximum at Baseline and all visits through Week 52 where NSAA is assessed for observed and changes from baseline NSAA total scores will be provided for fordadistrogene movaparvovec and placebo.
- The fordadistrogene movaparvovec and placebo LS means, standard error of each LS mean, and 95% CIs for the LS means along with the difference between the LS means (fordadistrogene movaparvovec minus placebo) and the corresponding standard error, two-sided p-value, and 95% CI will be provided for change from Baseline in NSAA total score for Week 52 and all visits through Week 52 where NSAA is assessed.

Graphical displays:

- The fordadistrogene movaparvovec and placebo LS means, and 95% CIs for the LS means at each visit will be displayed graphically.

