6.5.3. Geographic Region

The following endpoints will be evaluated by geographic regions:

- Change from Baseline at Week 52 in the NSAA total score
- Change from Baseline at Week 52 in the 10 meter run/walk test velocity.
- Change from Baseline at Week 52 in the rise from floor velocity.

The geographic regions in this study will be categorized as North America, Europe, and Asia-Pacific.

Analysis:

- Analysis set: FAS ([Section 4](#)).
- Analysis methodology:

For each geographic region strata separately, change from baseline will be analyzed using an MMRM approach ([Section 5.2.1.1](#)) including fixed effects for treatment group (categorical variable), visit (ordered categorical variable), and treatment group by visit interaction with additional fixed effects for baseline (continuous variable) and baseline by visit interaction, with additional fixed effects for screening age covariate (continuous variable) and screening age by visit interaction

For each geographic region strata, estimates of the mean changes from Baseline, standard error of each LS mean, and 95% confidence intervals for fordadistrogene movaparvovec and placebo will be provided for each visit along with the mean treatment group difference and the corresponding standard error two-sided p-value, and two-sided 95% confidence interval for the mean difference at each visit.

- Intercurrent events and missing data: All available data in the reporting period will be included. The intercurrent events and missing data will be handled as described in [Section 2.2.1](#) and [Section 2.2.2](#) accordingly.
- For each geographic region strata separately, the summary for each endpoint will be performed the same way as described in the corresponding main analysis in [Section 6.1](#) and [Section 6.2](#). No plots will be produced for these analyses.

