Change from Baseline at Week 52 in the NSAA total score	Supplementary	FAS plus siblings	All available data will be included Missing data will not be explicitly imputed	MMRM with additional fixed effects for Baseline NSAA total score, Screening age covariate, Baseline NSAA total score by visit interaction, and Screening age covariate by visit interaction
Change from Baseline at Week 52 in the NSAA total score	Screening age strata subset Summary	FAS	All available data will be included Missing data will not be imputed	Not applicable (N/A)
Change from Baseline at Week 52 in the NSAA total score	Screening age strata subset	FAS	All available data will be included Missing data will not be explicitly imputed	For each Screening age strata separately, MMRM with additional fixed effects for Baseline NSAA total score, and Baseline NSAA total score by visit interaction.
Change from Baseline at Week 52 in the NSAA total score	Screening age strata subset The p-value for the Screening age strata interaction term	FAS	All available data will be included Missing data will not be explicitly imputed	NSAA main analysis (MMRM) subset on Screening age strata and MMRM with additional fixed effects for Baseline NSAA total score, Baseline NSAA total score by visit interaction, Screening age strata, Screening age strata by visit interaction, and Screening age strata by treatment group interaction.
Change from Baseline at Week 52 in the NSAA total score	Baseline NSAA total score subset Summary	FAS	All available data will be included Missing data will not be explicitly imputed	Not applicable (N/A)

090177e1a0727983\Approved\Approved On: 16-Apr-2024 16:39 (GMT)

Endpoint	Analysis Type	Population	Data Inclusion and Rules for Handling Intercurrent Events and Missing Data	Analysis Model
Change from Baseline at Week 52 in the NSAA total score	Baseline NSAA total score subset	FAS	All available data will be included Missing data will not be explicitly imputed	For each baseline NSAA total score strata separately, MMRM with fixed effects for treatment group, visit, and treatment group by visit interaction with additional fixed effects for screening age covariate and screening age by visit interaction.
Change from Baseline at Week 52 in the NSAA total score	Geographic region subset Summary	FAS	All available data will be included Missing data will not be explicitly imputed	Not applicable (N/A)

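### The MMRMs fitted within each age stratum omit continuous age, which the main model and the other subgroup MMRMs keep; the possible loss is small

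*SAP*

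**What the plan says.** Section 3.4.1 sets the default for age: "The participant's Screening age rather than Screening age stratum will be used in all efficacy analyses, unless specified otherwise". The main NSAA model in Section 6.1.1.1 follows it, with "Screening age (continuous variable), Baseline NSAA total score by visit interaction, and Screening age covariate by visit interaction". The main models for the two velocities (6.2.4.1) and for actigraphy (6.3.2) have the same structure.

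Section 6.5.1 announces an exception, "where the model will be handled in a different way as below". Within each age stratum it uses an MMRM "with additional fixed effects for Baseline(continuous variable), and Baseline by visit interaction". Appendix 1 agrees for the NSAA total score: "For each Screening age strata separately, MMRM with additional fixed effects for Baseline NSAA total score, and Baseline NSAA total score by visit interaction". No reason is given.

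The neighbouring models differ:
- Section 6.5.2 (split at the median baseline NSAA) drops Baseline and keeps age and age by visit.
- Section 6.5.3 (region) keeps Baseline and also age, "with additional fixed effects for screening age covariate (continuous variable) and screening age by visit interaction".
- The interaction MMRM in 6.5.1 replaces continuous age by "Screening age strata (binary variable), Screening age strata by visit interaction, and Screening age strata by treatment group interaction".
- For both skills endpoints within the same age strata, Appendix 1 keeps a Screening age term.

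**The concern.** Splitting at age 6 does not remove age as a source of variation, because each stratum still runs over two years. The plan treats age as related to outcome. It stratifies randomisation on age (2.3), adjusts for it in the main model (6.1.1.1), and adds a sensitivity analysis on whether age is taken at screening or at dosing (6.1.1.5).

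Two things are given up. One is whatever precision continuous age could still add within a stratum. The other is comparability: the stratum estimate comes from a different covariate set than the overall estimate, so a difference between them mixes a change of population with a change of model. The same boys in the same strata would also be age-adjusted for skills but not for NSAA total score, the velocities or cadence.

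**Working it through.** **1. The plan's own figure.** Section 2.3.1 gives a difference of 3.0, SD 3.5, two-sided alpha 0.05, 99 participants, 3 dropouts and 98% power. Under the normal approximation with 64:32 evaluable, 3.0 / (3.5 × √(1/64 + 1/32)) = 3.96 and Φ(3.96 − 1.96) = 97.7%. With 66:33 the result is 98.0%. A simulation of the three-look design with looks at 30, 60 and 99 gives 97.1% at 96 evaluable. The 98% is reproduced to within about one point, so SD 3.5 is used below.

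**2. Stratum size.** Section 2.3 caps either stratum at 55% of dosed participants, so each holds about 0.45 × 99 = 45 to 0.55 × 99 = 54 boys. Half of 96 evaluable is 48, or 32:16 under 2:1 allocation.

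**3. Without age.** SE = 3.5 × √(1/32 + 1/16) = 1.07. With 45 df the 95% half-width is 2.16.

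**4. With age.** Let R² be the share of within-stratum residual variance that age explains. Allowing for the lost degree of freedom and for chance imbalance,

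ratio of CI widths = √[(1 − R²)(1 + 1/43)] × t(44)/t(45) ≈ 1.012 × √(1 − R²).

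The SAP gives no age slope, so the slope is an assumption. For age uniform over two years, R² = (slope × 2/√12)² / 3.5².

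| Assumed slope (points per year) | R² | CI width ratio | Half-width |
|---|---|---|---|
| 0 | 0 | 1.012 | 2.18 |
| 1 | 0.027 | 0.998 | 2.15 |
| 1.5 | 0.061 | 0.981 | 2.12 |
| 2 | 0.109 | 0.956 | 2.06 |

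Break-even is at R² of about 0.024.

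**5. A second route.** If age is uniform over 4 to 8 years with a linear effect, a quarter of the age variance lies within strata: (2²/12)/(4²/12) = 0.25. An overall R² then becomes 0.25R²/(1 − 0.75R²) within a stratum. Overall values of 0.10, 0.20 and 0.30 become 0.027, 0.059 and 0.097, and CI width changes by −0.2%, −1.8% and −3.8%.

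**6. Chance imbalance.** Within-stratum age SD is 2/√12 = 0.58 years. The difference in mean age between arms has SD 0.58 × √(1/32 + 1/16) = 0.18 years. At slopes of 1 to 2, that is a typical shift of 0.18 to 0.35 points, against an SE of 1.07.

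**The case against.** The omission is prespecified and allowed. Section 3.4.1 permits exceptions, Section 6.5.1 announces one, and Appendix 1 also leaves age out of the per-stratum MMRM. There is also a visible pattern: the NSAA split drops Baseline, the age split drops age, and region, which is neither covariate, keeps both. This explains much of the design. It does not explain the skills rows in Appendix 1, which keep age inside the same age strata.

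The size rests on a slope that the SAP does not supply. A slope of 2 over ages 4 to 8 would mean that age explains (2 × 4/√12)²/3.5² = 44% of total variance if 3.5 is the total SD, so the upper end is extreme. Baseline is already in the model and may absorb part of any age effect. Both points stand, and they push the likely gain towards the low end of the range.

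A reader might infer that age is dropped where samples are smallest. It is not: three regions average 99/3 = 33 boys, so at least one has 33 or fewer, and the regional models carry the fuller covariate set. A reader might also infer that these are the only models without continuous age. They are not: the interaction models for the MMRM and skills endpoints in 6.5.1 use the binary stratum instead.

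**Conclusion.** The point holds as a minor inconsistency with a small possible cost. The per-stratum MMRMs leave out a covariate that the plan treats as prognostic and keeps in the main model, in the other two subgroup MMRMs and in the Appendix 1 skills models for the same strata.

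Adding it changes CI width by between about 1% wider and about 5% narrower. This assumes a slope of 0 to 2 points per year, uniform age, SD 3.5 and 48 boys per stratum. Adjustment would also remove chance age imbalance from the stratum estimate and align the model with the primary one.

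A reader might infer that the subgroup estimates are biased. The documents do not support that. Randomisation is stratified at age 6, so each stratum is itself a randomised comparison, and chance imbalance is already reflected in the SE. The subgroup analyses lie outside the testing hierarchy in Section 5.1, so no error rate, power figure or primary conclusion changes.

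**What to change.** Add Screening age (continuous) and Screening age by visit to the per-stratum MMRMs in Section 6.5.1, and make the same change in the matching Appendix 1 rows for NSAA total score, 10 meter run/walk velocity and rise from floor velocity. Cadence has no separate per-stratum row in Appendix 1, so for that endpoint the change is in 6.5.1. The interaction model can stay as it is, since its purpose is to test the binary stratum.

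If the sponsor prefers to leave age out, one sentence in 6.5.1 should say why, and why the skills models in the same strata keep it.

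The cost is two model terms on data already collected, and about one degree of freedom at Week 52.

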2.3.1. Sample Size Determination

The sample size of 99 participants in the FAS (see Section 4) is based on the primary efficacy endpoint of change from Baseline at Week 52 in the NSAA total score. The above sample size (assuming 3 participants will drop out of the study prior to Week 52) will provide 98% power to detect a treatment difference (fordadistrogene movaparvovec minus placebo) of 3.0. These calculations are based on $\alpha=0.05$ (two-sided), a 3-look group-sequential design with a gamma family (-1) spending function to determine the efficacy boundary, a gamma family (-4) spending function for the non-binding futility boundary, a common standard deviation of 3.5, and using the normal approximation of the test statistic for the comparison between two means.

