5.2.1. Analyses for Continuous Endpoints

5.2.1.1. Mixed Model Repeated Measures (MMRM)

The MMRM model assumes that all random effects in the model are normally distributed. The dependent variable will be the specific endpoint and the model will include fixed effects terms for:

- Treatment group (as a categorical variable);
- Scheduled visit time point (as an ordered categorical variable);
- Interaction between treatment group and scheduled visit time point.

Additional fixed effects (eg, covariates and interaction effects) to be included in the model for specific analyses are given in [Section 6](#). Participant will be the random effect in the model. The restricted maximum likelihood (REML) estimation method will be used with an unstructured covariance matrix to describe the correlation among different visits from the same participant. If there are convergence issues with the model, the following structures will be considered in the order listed below until convergence is obtained:

1. Spatial Power (SP);
2. Autoregressive-1 (AR(1));
3. Compound Symmetry (CS).

The Kenward-Roger degrees of freedom will be used.

The model-adjusted estimates for the endpoint for each treatment group at each specified time point will be provided using the least squares (LS) means calculated based on the average continuous covariate values, standard error of each LS mean, and their 95%

confidence intervals (CIs). The difference in LS means (fordadistrogene movaparovec minus placebo) will be provided at each specified time point along with corresponding standard error, two-sided p-values (unadjusted for multiplicity), and 95% CIs (unadjusted for multiplicity).

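### For the four repeated-measures endpoints, the age-stratum interaction p-value tests an average over Weeks 9 to 52 and not effect modification at Week 52.

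*SAP*

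**What the plan says.** SAP 6.5.1 lists six endpoints, all defined at Week 52; the first is "Change from Baseline at Week 52 in the NSAA total score". Four of them (NSAA total score, 10 m run/walk velocity, rise from floor velocity, 95th percentile of cadence) are analysed by MMRM in two ways.

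- **Separate models by stratum.** These give treatment differences with SE, p-value and 95% CI at every visit.
- **One combined model.** It takes the base terms of 5.2.1.1, which include "Interaction between treatment group and scheduled visit time point", and adds baseline, baseline by visit, and "Screening age strata (binary variable), Screening age strata by visit interaction, and Screening age strata by treatment group interaction". The output is described as: "The p-value for the Screening age strata interaction term will be provided". No visit is named.

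Appendix 1 repeats the structure for all four endpoints: "Screening age strata by visit interaction, and Screening age strata by treatment group interaction". The visits are Weeks 9, 18, 35 and 52 (6.1.1.1, 6.2.4.1, 6.3.2).

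The other two endpoints, the skill counts, are modelled at Week 52 only, so their interaction p-values already refer to Week 52.

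**The concern.** Without a stratum-by-treatment-by-visit term, the difference in treatment effect between the strata is forced to be the same at every visit. The p-value then answers whether the visit-averaged effect differs by age stratum. The endpoint asks whether the Week 52 effect differs.

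The combined model also disagrees with the analyses around it. The separate models let the visit profile differ freely between strata, and the combined model forbids this. Its p-value will be printed beside Week 52 estimates that it does not compare. Within one list of six endpoints, four p-values would refer to a visit average and two to Week 52.

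Age below 6 or at least 6 years is the randomisation stratum. Sections 6.5.2 and 6.5.3 plan no interaction test, so this is the only between-subgroup test planned for these four endpoints, the primary included. A null result could be read as a consistent Week 52 effect across ages, and a positive one as a Week 52 difference, when neither was tested.

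**Working it through.** **Inputs from the SAP.** "The sample size of 99 participants in the FAS", difference 3.0, common SD 3.5, two-sided alpha 0.05, 3 dropouts (2.3.1); 2:1 allocation and at most 55% of dosed participants in either stratum (2.3). On covariance, 5.2.1.1 says: "The restricted maximum likelihood (REML) estimation method will be used with an unstructured covariance matrix".

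**Inputs assumed.** Equal strata, giving cells of 33/33 (active) and 16.5/16.5 (placebo), and complete data. SDs by visit and correlations are not in the SAP and are varied below. Visit times are the target days 60, 120, 240 and 360 (Appendix 2.1).

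**The plan's own figure.** SE = 3.5 × √(1/66 + 1/33) = 0.746; 3.0/0.746 = 4.02; power = Φ(4.02 − 1.96) = 98.0%. With 96 participants it is 97.7%, and with three looks 96.8-97.5%. The stated 98% is reproduced within about a point.

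**What the constant term estimates.** With between-visit covariance S, generalised least squares gives a weighted average of the four visit-specific interactions, with weights w = S⁻¹1 / (1′S⁻¹1). Its variance is k / (1′S⁻¹1), where k = 2 × (1/33 + 1/16.5) = 0.182.

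**Reference: a Week 52 contrast.** SE = 3.5 × √0.182 = 1.49. For a 4-point interaction, 4/1.49 = 2.68 and power = Φ(2.68 − 1.96) = 76%, whatever happens at earlier visits.

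**One case in full: flat SD 3.5, compound symmetry, correlation 0.5.** Each visit has weight 0.25. SE = √(0.182 × 12.25 × (1 + 3 × 0.5)/4) = 1.18.

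- A 4-point interaction building linearly is estimated as 4 × (60 + 120 + 240 + 360)/(4 × 360) = 2.17; 2.17/1.18 = 1.84; power 45%.
- An interaction of 3, 2, 1, 0 points (none at Week 52) is estimated as 1.5; 1.5/1.18 = 1.27; flagged 25% of the time.

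**Range over assumptions.** The flat rows use compound symmetry, AR(1) and spatial power with correlation 0.5-0.8 (spatial power per 60 or 120 days). The rising rows use S = 12.25 × [e × CS(0.5) + (1 − e) × min(tᵢ, tⱼ)/360] with e = 0, 0.25, 0.5 and 0.75. This is a variance that accumulates with time and reaches SD 3.5 at Week 52.

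| | Weight, Week 52 | Weight, Weeks 9+18 | Power, linear to 4 points | 3, 2, 1, 0 flagged | Power, constant 4 points |
|---|---|---|---|---|---|
| Flat SD | 0.25-0.43 | 0.45-0.50 | 35-69% | 19-32% | 83-99% |
| Rising | 0-0.16 | 0.64-1.00 | 19-37% | 38% to nearly 100% | 95-100% |
| Week 52 contrast | 1 | 0 | 76% | 5% | 76% |

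Other rising-SD structures spread further. With 96 participants and SD rising from 2.8 or 2.2 to 3.5, the Week 52 weight runs from −0.19 to 0.27, and power for the linear pattern from 5% to 44%, against 75% for the contrast.

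**Check against the full design**, with all listed fixed effects and AR(1) correlation 0.8: a 4-point interaction present only at Week 52 gives a coefficient of 1.67 with flat SD (1.67/4 = 0.42, matching the weight) and 0.29 with SD rising from 2.2 to 3.5.

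**The case against.** **Effect shape.** Pooling over visits does not always lose. If the interaction is the same at all visits, the term as written has more power than the Week 52 contrast (83-100% against 76%). Nothing in the SAP says how fast the effect develops. This stands, and it is the price of the change.

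**Early visits.** A reader might infer that the p-value mostly tests Weeks 9-18. The documents do not support that as a general statement. It needs the variance of change to rise over visits, which is plausible in a progressive disease but not stated. The only SD given is 3.5, and with a flat SD Weeks 9 and 18 together carry about half the weight.

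**Only formal check.** A reader might also infer that this is the only formal test of age-related effect modification. It is not: the two skill-count interactions are tested at Week 52. The statement holds only for the four MMRM endpoints.

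**Consequence.** The p-value is outside the fixed testing sequence of 5.1. The separate models report Week 52 differences and SEs on disjoint participants, so a reader can compute the between-stratum difference by hand. The 4-point illustration exceeds the planned overall effect of 3.0, and for 2 points even the Week 52 contrast has only 27% power (2/1.49 = 1.34; Φ(1.34 − 1.96)). All of this stands and limits the weight of the point. It does not make the planned p-value a Week 52 test.

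**Conclusion.** The point holds for the four MMRM endpoints. The interaction p-value tests a weighted average over Weeks 9, 18, 35 and 52, while the endpoint is Week 52. That follows from the listed model terms and needs no assumption.

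The size does depend on assumptions. In every covariance tried, Week 52 had less than half the weight: about 25-43% with a flat SD, and little, none or slightly negative weight when variance rises with time. Even in the flat case, a linearly building 4-point interaction is detected less often than with the Week 52 contrast (35-69% against 76%), and an interaction that has vanished by Week 52 is flagged 19-32% of the time.

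This is worth correcting before the analysis. It does not touch the primary test or Type I error control.

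**What to change.** In SAP 6.5.1, add screening age stratum by treatment group by visit to the combined MMRM, keeping the two-way terms. Replace the unnamed interaction p-value with the stratum-by-treatment contrast at Week 52, reported with estimate, 95% CI and p-value. Make the same change in the Appendix 1 interaction rows for NSAA total score, 10 m run/walk velocity, rise from floor velocity and 95th percentile of cadence. The skill-count models need no change.

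The cost is SAP wording and three more fixed-effect parameters (four visits less one), plus some loss of power if the interaction is in truth constant over visits. No new data and no alpha are needed. If the visit-averaged interaction is also of interest, it can be kept as a second result, labelled as such.
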